2.3. Follow-up Assessments (Visits 20 to 24)

Study Schedule Protocol I8G-MC-LMDD - MAD Treatment Period; Follow-up Assessments (Visits 20 to 24)

[figure not shown]
| Visit | V20 | V21 | V22 | V23 | V24 | ED |
|---|------------------------------|-----|-----|-----|-----|----|
| Day Relative to First Dose (for 25-week treatment phase)^a | 189 | 203 | 231 | 259 | 287 | |
| Week (for 25-week treatment)^a | 27 | 29 | 33 | 37 | 41 | |
| Day Relative to First Dose (for 49-week treatment phase)^a | 351 | 365 | 393 | 421 | 449 | |
| Week (for 49-week treatment)^a | 51 | 53 | 57 | 61 | 65 | |
| Tolerance Interval for Visit (days) | ±7 | ±7 | ±7 | ±7 | ±7 | |
| Imaging | | | | | | |
| MRI ^d | | | | X | | X |
| Flortaucipir F 18 PET ^{c,d} | X (if not done at V13 or 19) | | | | | X |
| Laboratory Assessments (central laboratory unless otherwise noted) | | | | | | |
| Lumbar puncture ^{c,e,g} | X (if not done at V13 or 19) | | | | | X |

Notes:

- (i) Patients who have completed at least the 25-week treatment period will be followed up for 16 weeks after completion of dosing (Visits 20 to 24) and will return to the investigational site for safety assessments, PK, and plasma tau (PD) sampling on Visits 20 to 24 as per the Schedule of Activities.
- d The flortaucipir F 18 PET scan should be conducted at Visit 13 should the patients follow the 25-week treatment or at Visit 19 for the 49 week treatment period. The flortaucipir F 18 PET scan should be completed at Visit 20 if the patient discontinues treatment after Visit 13 and before Visit 19. Patients permanently discontinued from study treatment due to initiation of a prohibited medication known to prolong the QT interval should not have an ED flortaucipir F 18 scan unless the scan can be performed prior to initiation of the prohibited medication. Patients who have continued on study after introduction of a drug known to prolong QT interval (with sponsor approval) need a minimum of 14 days or 5 half-lives, whichever is longer, without that drug prior to the flortaucipir scan. If patients have had a flortaucipir F 18 PET scan at Visit 13 (as per amendment (b)), they will not be required to have another scan at Visit 20.
- e Coagulation test results should be reviewed before each LP. Concomitant medications should be reviewed to ensure that no changes to anticoagulation or antiplatelet therapy have occurred since the last coagulation test. The coagulation test is required up to 2 weeks prior to the LP, if LP is performed at Visit 20.
- g The LP should be conducted at Visit 13 should the patients follow the 25-week treatment or at Visit 19 for the 49-week treatment period. The LP should be completed at Visit 20 if the patient discontinues treatment after Visit 13 and before Visit 19.

5.1. Overall Design

Previous diagram:

Revised diagram:

[figure not shown]

Figure LMDD.1. Illustration of study design.

5.1.2. Dosing for all Cohorts

Patients will receive their study drug at the investigational site after all predose procedures have been completed and must be observed closely for at least 4 hours following each infusion of LY3303560 for the first 6 infusions. After the first 6 infusions, a minimum post-infusion observation time of 2 hours will be required for all subsequent infusions, and remain in the investigative site for at least 8 hours, after each administration. If any patient shows symptoms of an infusion reaction, the observation time will be increased to a minimum of 8 hours for that infusion and all subsequent infusions.

5.1.3. Treatment Phase

Each cohort will consist of 8 patients randomised (6 LY3303560: 2 placebo) to a 25-week MAD treatment period (7 doses), after which they will be given the option of continuing the treatment up to 49 weeks (up to 6 further doses, Visits 14 to 19). Patients who have completed at least the 25-week treatment period will be followed up for 16 weeks after completion of dosing (Visits 20 to 24) ~~and will return to the investigational site for safety assessments and PK and biomarker sampling throughout Visits 20 to 24 as per the Schedule of Activities (see in Section 2 for the Schedule of Activities).~~

7.1. Treatment Administered

[...]

The minimum time for close observation at the investigative site following dosing is 4 hours for the first 6 IV infusions and 2 hours for subsequent IV infusions. If any patient shows symptoms of an infusion reaction, the observation time will be increased to 8 hours for that infusion and all subsequent infusions. The site must have resuscitation equipment, emergency drugs, and appropriately trained staff available during dosing and while patients are under observation after dosing.

Leo Document ID = 14983b1d-b9d2-43e0-b83d-6c209b7b1b15

Approver: PPD

Approval Date & Time: 02-May-2018 17:37:25 GMT

Signature meaning: Approved

Approver: PPD

Approval Date & Time: 02-May-2018 17:37:25 GMT

Signature meaning: Approved

## 2. Revision History

SAP Version 1 was approved prior to first patient visit and prior to unblinding

SAP Version 2 was approved prior to prior to unblinding and final database lock. Changes reflect the changes made to the LMDD protocol as defined in LMDD (b) and (d).

Briefly, in amendment (b), the higher dose cohorts of LY3303560 (700 and 1400 mg) have been removed based on an update to the PK/PD model originally used to predict the LY3303560 efficacious dose range. In addition, the duration of dosing in the LMDD study has been reduced from 12 months to 6 months, based on emerging longitudinal and baseline data using tau positron emission tomography (PET) imaging, which suggests that the Part B of the study is now insufficiently powered to assess the effects of LY3303560 on progression of tau pathology using the tau tracer flortaucipir F 18 PET over 12 months. However the effects using the tau tracer on tau pathology of repeated every 4 week (Q4W) administrations in patients over approximately 6 months (7 doses), with the option of extending the treatment period to up to 12 months (up to 6 further doses), in the two remaining doses of Part A.

A decision was made by the team to not implement amendment c because the cohort 2 subjects would have had a LP at V13 per amendment b after which amendment c would be implemented and another LP would have been required at V20 per amendment c. This would have meant an extra LP for these subjects.

The overall changes made to protocol amendment b to create LMDD (d) are as follows:

- In the Schedule of Activities in Section 2, the lumbar puncture at Visit 13, which was removed in protocol amendment (c), has been reinstated to accommodate patients who are following the 25-week dosing period. A flortaucipir F 18 PET scan has been added to Visit 13 for the same reason.
- The Schedule of Activities in Section 2 has been amended to show the LP and flortaucipir F 18 PET scan are not required at Visit 20 for patients who have had an LP or PET scan at Visits 13 or 19. A flortaucipir F 18 PET scan has been added to Visit 19 for patients following the 25-week treatment period.
- The Schedule of Activities (Section 2) has been amended to show that, after a patient has had 6 infusions with no infusion reaction, the observation period for subsequent infusions has been reduced to 2 hours. However, should any infusion reaction occur for any patient, the monitoring period will be increased to at least 8 hours for all subsequent infusions. To date, there have been no infusion reactions observed in 9 subjects in Cohort 1 (70 mg LY3303560) who have reached at least 6 months of dosing and 9 subjects in Cohort 2 (210 mg LY3303560) who have reached at least 3 months of dosing.

### 3. Study Objectives

Primary
 
The primary objective of this study is to assess the safety and tolerability after 16 weeks of multiple doses of LY3303560 in patients with MCI due to AD or mild to moderate AD
	
Safety and tolerability will be assessed by monitoring treatment-emergent adverse events (TEAEs)

Secondary
 
 
• To assess the PK of LY3303560 in serum following multiple IV doses of LY3303560 in patients with MCI due to AD or mild to moderate AD
 
	
Maximum serum concentration (<math>C_{max}</math>) and the area under the serum concentration time curve during the dosing interval (<math>AUC_{\tau}</math>)

Exploratory Objectives
 
 
• To evaluate the effects of multiple doses of LY3303560 on cognitive function in patients with MCI due to AD or mild to moderate AD
 
• To evaluate the effects of multiple doses of LY3303560 on brain atrophy in patients with MCI due to AD or mild to moderate AD
 
• To evaluate the effects of multiple doses of LY3303560 on brain functional connectivity in patients with MCI due to AD or mild to moderate AD
 
• To evaluate the immunogenicity of multiple doses of LY3303560 in patients with MCI due to AD or mild to moderate AD
 
• To evaluate the effects of multiple doses of LY3303560 on plasma and CSF biomarkers in patients with MCI due to AD or mild to moderate AD
 
• To evaluate the effects of multiple doses of LY3303560 on tau pathology using the tau tracer flortaucipir F 18 in patients with MCI due to AD or mild to moderate AD
 
• To determine the CSF concentration of LY3303560 following multiple IV doses in patients with MCI due to AD or mild to moderate AD
 
	
ADAS-Cog14, ADCS-MCI-ADL24, NTB, MMSE, dCDT
 
Quantitative measures of brain atrophy derived from volumetric MRI scans
 
Quantitative measures of brain functional connectivity derived from functional MRI scans
 
Detection of anti-drug antibodies (ADA)
 
Plasma tau concentration; CSF concentration of tau, p-tau, A<math>\beta</math>1-42, and neurogranin
 
Quantitative endpoints from flortaucipir F 18 PET scans
 
Mean LY3303560 concentrations in CSF

Exploratory Objectives (continued)	


• To explore the safety and tolerability of LY3303560 in Japanese subjects in relation to non-Japanese subjects

• To explore the PK of LY3303560 in Japanese subjects in relation to non-Japanese subjects

	
Safety and tolerability will be assessed by monitoring TEAEs
 
<math>C_{max}</math> and <math>AUC\tau</math>

## 4. Study Design

This is a Phase 1b, multi-site, patient- and investigator-blind, placebo-controlled, parallel-group study in patients with MCI due to AD or mild to moderate AD to assess the safety, tolerability, PK and PD following multiple IV doses of LY3303560.

The planned doses of LY3303560 are: 70 and 210, mg; however, dose levels may be adjusted based on emerging data from Study LMDA and from this current study, if indicated.

Dose escalation decisions will be made following a review of the safety data from a minimum of 4 patients having received at least 2 doses of LY3303560 and 1 patient having received at least 2 doses of placebo at the prior dose level. The subsequent cohort will not begin dosing until all 8 patients from the previous cohort have started dosing. For each cohort, IADs for review of safety data, including ADA titres (if available), and PK data will be conducted at 16 weeks to evaluate the safety, PK and PD of LY3303560 at steady-state.

### 4.1. Method of Assignment to Treatment

Assignment to treatment groups will be determined by a computer-generated random sequence within each dose cohort using an interactive web response system (IWRS).

For Cohorts 1 to 2, up to 12 patients may be enrolled so that approximately 8 patients per cohort (6 LY3303560: 2 placebo) provide data to Day 113. The randomization will be such that the placebo assignments for the cohorts enrolling Japanese and non-Japanese subjects will be balanced between these 2 populations.

## 5. A Priori Statistical Methods

### 5.1. General Considerations

Pharmacokinetic analyses will be conducted on the full analysis set (not including placebo). This set includes all data from all subjects receiving at least one dose of the investigational product.

Safety analyses will be conducted for all enrolled subjects who took study medication, whether or not they completed all protocol requirements.

Additional exploratory analyses of the data will be conducted as deemed appropriate. As this is a Phase 1 study and there will be no formal statistical hypothesis testing, any changes to the planned analysis will not necessitate a protocol amendment and will be detailed in the study report. Summary statistics, data tabulations, and data graphs by ethnicity (Japanese and non-Japanese, and combined) will be provided as appropriate.

Safety reporting will be conducted by Covance; with the exception of QTcF statistical analyses which will be conducted by Eli Lilly. All drug effects, PK, PD, imaging, cognition and exploratory reporting and analyses will be conducted by Eli Lilly.

Where two cohorts are given the same dose and formulation the patients will be pooled together and reported under the same dose levels. Placebo will be pooled across all cohorts.

In recognition that there are now only two dose cohorts in this study, any statistical models detailed in the analysis plan may still be carried out in order to estimate parameters, in particular where changes from baseline are being considered. Without recourse to statistical models, only those patients with both baseline and at least one post-baseline measurement can be included in any summary. Estimates from statistical models may provide additional information, if interpreted appropriately.

#### 5.1.1. *Handling of Dropouts or Missing Data*

Subjects or patients who discontinue may be replaced at the discretion of the sponsor and investigator. The ethnicity of the replacement subject (Japanese or non-Japanese) should match the ethnicity of the discontinued patient, where possible. Replacement patients will be allocated the same treatment as the dropout patient.

There will be no imputation of missing data.

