5.2. Number of Participants

In each cohort, up to 12 patients may be enrolled so that approximately 8 patients per cohort (6 LY3303560: 2 placebo) provide safety and PK data to steady state.

A maximum of 24 patients will be enrolled.

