The IMP will be manufactured in accordance with good manufacturing practices and will be labeled according to applicable local regulatory requirements.

7.2. *Method of Treatment Assignment*

A patient number will be assigned to each patient after the ICF is signed and dated. This identification number must appear on all patient-related documents. Assignment to treatment groups will be determined by a computer-generated random sequence within each dose cohort using an interactive web response system (IWRS).

7.2.1. *Timing of Doses*

Doses should be administered at approximately the same times on each day. The actual time of all dose administrations will be recorded in the patient's CRF. For IV infusions, the actual duration time of the infusion will be recorded in the CRF. If the infusion is interrupted or terminated, this should be recorded in the CRF.

7.3. *Blinding*

This is a patient- and investigator-blind study.

To preserve the blinding of the study, a minimum number of Lilly personnel will see the randomisation table and treatment assignments before the study is complete.

Investigative site pharmacists or pharmacy staff will be unblinded due to their involvement in dose preparation. In order to maintain the blind, these unblinded investigative site staff will not be involved in clinical assessments of patients or general conduct of the study.

Emergency unblinding for AEs may be performed through the IWRS. This option may be used ONLY if the patient's well-being requires knowledge of the patient's treatment assignment. All actions resulting in an unblinding event are to be recorded and reported by the IWRS.

If a patient's study treatment assignment is unblinded, the patient must be discontinued from the study, unless the investigator obtains specific approval from a Lilly clinical pharmacologist or clinical research physician (CRP) for the patient to continue in the study. During the study, emergency unblinding should occur only by accessing the patient's emergency code.

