10.1. Sample Size Determination

A total of 24 patients may be enrolled to ensure 16 complete the study. The sample size is customary for Phase 1 studies evaluating safety, PK and/or PD parameters.

It is expected that at least 4 Japanese patients will be enrolled into the study. Patients will be stratified by Japanese/non-Japanese but not by disease severity at randomisation.

Patients who are randomised but do not complete the study may be replaced to ensure that enough patients complete the study (see Section 5.2).

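### SAP 5.1.1 gives a replacement the dropout's treatment even after a broken code, and protocol 10.1 ties replacement to finishing the study although the data target is Day 113

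*SAP*

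**What the plan says.** **Allocation of replacements.** Protocol 7.2 and SAP 4.1 describe one method only: a computer-generated random sequence within each cohort, run through the IWRS. SAP 5.1.1 adds a rule that the protocol does not contain: "Replacement patients will be allocated the same treatment as the dropout patient". It also says "Subjects or patients who discontinue may be replaced at the discretion of the sponsor and investigator", and asks that the replacement match the dropout on Japanese or non-Japanese status where possible.

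**Broken codes.** Protocol 7.3 makes the investigator solely responsible for deciding whether an emergency code break is warranted. It says that if a patient's "study treatment assignment is unblinded, the patient must be discontinued from the study", unless the sponsor's clinical pharmacologist or physician approves continuation. Neither document exempts these patients from the same-treatment rule, or says that the site is kept unaware of which dropout a replacement stands for.

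**Who may be replaced, and to reach what.** Protocol 10.1 says "A total of 24 patients may be enrolled to ensure 16 complete the study" and "Patients who are randomised but do not complete the study may be replaced to ensure that enough patients complete the study", with a cross-reference to 5.2. Protocol 5.2 says "In each cohort, up to 12 patients may be enrolled" so that about 8 (6 active, 2 placebo) give safety and PK data to steady state. Protocol 5.4 places the minimum safety and PK data at Day 113. SAP 4.1 says the same: "approximately 8 patients per cohort (6 LY3303560: 2 placebo) provide data to Day 113".

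**The concern.** There are two separate issues.

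The first is concealment. A code-broken patient becomes, by default, a patient who can be replaced, and the replacement's arm is then fixed by an arm that somebody at the site has seen. Protocol 5.4 includes a blinded placebo so that the safety and PD data are assessed without bias. The primary endpoint is TEAEs. The investigator judges relatedness (protocol 9.2), and events are tabulated by severity and by the investigator's view of association (protocol 10.3.1.1, SAP 5.4.1). Relatedness also enters the rules for halting dosing and escalation in protocol 7.4.1. The protocol guards against unblinding by inference elsewhere: 5.1.4 requires at least 2 Japanese patients in a cohort for that reason. SAP 5.1.1 has no comparable guard.

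The second is the reference point for replacement. A patient who leaves after Day 113 has given the data that 5.2, 5.4 and SAP 4.1 ask for, yet may be replaced under 10.1. Each such replacement would expose one more person to study drug, lumbar puncture and PET without adding to the Day 113 data that those sections call for.

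**Working it through.** **1. The plan's own figures.** 2 cohorts × 12 = 24 and 2 cohorts × 8 = 16, as stated. The allowance is 24 − 16 = 8 places, 4 per cohort, which covers a loss of 1 − 16/24 = 33.3%. No power calculation is involved. The 16 in 10.1 equals 2 × 8 from 5.2, so the same number carries two different completion criteria.

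**2. What an investigator could infer.** With a fresh code at 6:2, the best guess of a patient's arm is right 6/8 = 75% of the time. Under the same-treatment rule it is right 100% of the time if the investigator knows three things: the dropout's arm, the pairing and the rule. Suppose that, for a code-broken dropout, the pairing and the rule are both known with probability q. The documents do not give q, so the full range is shown:

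P(correct) = q + 0.75 × (1 − q)

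- q = 0: 75%
- q = 0.5: 0.5 + 0.375 = 87.5%
- q = 1: 100%

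For a dropout whose code was never broken, the rule alone leaves the figure at 75%.

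One such replacement is 1 of 6 active patients in a cohort, or 1 of 2 placebo patients. Placebo is pooled for analysis, so against the planned 2 + 2 it is 1 of 4.

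**3. Replacements under each reference point.** The last follow-up visit is Day 287 after 25 weeks of treatment and Day 449 after 49 weeks (protocol 2.3). The documents give no dropout rate, so annual rates p of 10%, 20% and 30% are assumed, with constant hazard h = −ln(1 − p)/365. Replacements needed for 16 patients to reach day d are 16/exp(−h × d) − 16.

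| Assumed annual dropout | To Day 113 | To Day 287 | To Day 449 |
|---|---|---|---|
| 10% | 0.5 | 1.4 | 2.2 |
| 20% | 1.1 | 3.1 | 5.1 |
| 30% | 1.9 | 5.2 | 8.8 |

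At 20%, moving from Day 113 to study completion adds 3.1 − 1.1 = 2.0 to 5.1 − 1.1 = 4.0 replacements. The 8.8 in the last cell could not occur, because only 8 places exist.

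**4. How much is still open.** The amendment (d) summary and SAP section 2 report 9 subjects in Cohort 1 with at least 6 months of dosing and 9 in Cohort 2 with at least 3 months. Both exceed 8. At most 12 − 9 = 3 places per cohort remain.

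**5. What an unlinked code does to the split.** Assume the next code is active with probability 0.75. After one active dropout, the patients providing data stay at 6:2 with probability 75%, and become 5:3 otherwise. After one placebo dropout they stay at 6:2 with probability 25%, and become 7:1 otherwise.

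**The case against.** The chain behind the inference is long. It needs an emergency code break, which 7.3 allows only when the patient's well-being requires it. It also needs no sponsor approval to continue, a discretionary decision to replace, and a rating investigator who knows both the pairing and the rule. The study is multi-site, the IWRS assigns treatment, and unblinded pharmacy staff are kept out of clinical assessments. The rule stands in the SAP alone, so an investigator working from the protocol may not know it. All of this stands, and it limits the point to a possible inference. What remains is that the investigator takes part in the replacement decision, matching on ethnicity can help reveal the pairing, and nothing in the text closes the route.

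Same-treatment replacement also has a real merit. It protects the 6:2 split and the balance of placebo between Japanese and non-Japanese patients that SAP 4.1 asks for. With two placebo patients per cohort, dropping the rule altogether would cost more than it gains.

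On the reference point, 10.1 is permissive and refers to 5.2, so it can be read as meaning the 5.2 target. That also stands: the defect is loose wording, mostly within the protocol.

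A reader might draw stronger conclusions that the documents do not support:

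- *A replacement for an unblinded patient is not blinded.* That requires knowledge of the pairing and the rule, which neither document establishes.
- *The protocol and SAP conflict over who decides.* The SAP names the sponsor and investigator; the protocol is silent.
- *Unblinding of the sponsor team at escalation reviews makes matters worse.* The study is patient- and investigator-blind by design, and 10.3.6 keeps the investigator blinded at those reviews.
- *A revealing event such as hypersensitivity gives the same clue.* This is hypothetical: no infusion reactions had been seen in the 9 + 9 subjects reported.

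**Conclusion.** Both points hold in a narrow form, and both are cheap to settle.

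SAP 5.1.1 leaves open a route by which an investigator could infer a replacement's arm after a code break, with the chance of a correct guess between 75% and 100% depending on an unknown q. No formal hypothesis tests are planned, so the consequence is possible bias in investigator-rated severity and relatedness for what would probably be no more than one patient, in a cohort where that is 1 of 6 active or 1 of 2 placebo.

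Protocol 10.1 uses a later reference point than 5.2, 5.4 and SAP 4.1. At an assumed 20% annual dropout with constant hazard, that is worth about 2 to 4 extra replacements. The maximum of 24 caps the number, and with 9 subjects already reported in each cohort little of it is still in play.

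**What to change.** 1. In SAP 5.1.1, keep same-treatment replacement as the general rule and add one sentence: a patient whose treatment code was broken is not replaced with the linked treatment, and any replacement takes the next unlinked IWRS code.
2. In protocol 10.1, replace study completion by provision of safety and PK data to Day 113, both in the target of 16 and in the replacement criterion, and limit replacement to patients who leave before Day 113.

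The cost is two short edits and one IWRS instruction. Among patients providing data, a cohort with a code-broken dropout may end at 7:1 or 5:3 instead of 6:2. The loss is most likely after a placebo dropout, where 6:2 survives with probability 25%. The Japanese/non-Japanese placebo balance may also suffer. Under the second change, fewer patients may reach the late exploratory assessments, because those who leave after Day 113 would not be replaced.
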